5.8.2. Prohibited Medications and Treatments

Subjects are required to discontinue and avoid using certain medications and treatments (see [Section 4.2, Inclusion Criteria](#) and [Exclusion Criteria](#), and [Appendix 3](#)). Subjects should be instructed at each visit to contact the study site investigator promptly if there are any intended changes or additions to concomitant medications.

All medications and treatments that could affect atopic dermatitis must be discontinued except oral antihistamines. Due to the potential to affect atopic dermatitis with ultraviolet light exposure, subjects must also avoid prolonged exposure to the sun and not to use tanning booths, sun lamps or other ultraviolet light sources during the study.

Subjects who received prior treatment with JAK inhibitors are to be excluded from the study.

Herbal medications with unknown properties or known beneficial effects for AD must be discontinued at least 4 weeks before the first dose of investigational product.

Restrictions on certain vaccinations are described in [Section 4.4.2](#).

The Pfizer study team is to be notified of any prohibited medications taken during the study. After consulting with the Medical Monitor, the investigator will make a judgement on the ongoing eligibility of any subject with prohibited medication use during the study.

6. STUDY PROCEDURES

Refer to the [Schedule of Activities](#) for a detailed list of study procedures as they should be conducted at each respective visit.

Due to possible need for PPD testing and chest radiograph, screening procedures may be performed over more than 1 visit in the 28 days prior to the Day 1 visit.

Visit windows are based on Day 1 visit. To assure consistency and reduce variability, all study visits should occur in the morning whenever possible. On days of study visits, subjects will receive their dose at the clinic during the visit.

Subjects are required to fast for at least 8 hours prior to all visits that include lipid profile panel testing (Day 1, Week 4, Week 12, and EOS). During the fasting period, subjects should refrain from all food and liquids (water and permitted non-study medications are allowed).

ECGs will be interpreted by a central reader for all visits.

Urine pregnancy test must be performed prior to dosing with the investigational product for female subjects of childbearing potential, including adolescents aged 12 years and older, regardless of whether they have experienced menarche, through to the EOS visit.

Prior to attending a study visit, subjects are allowed to shower and bathe but should not moisturize or apply emollient.

Refer to [Appendix 4](#) for guidelines on subject safety monitoring and discontinuation.

6.1. Visit 1, Screening

Subjects will be screened (Visit 1) within 28 days prior to administration of the investigational product to confirm that they meet the subject selection criteria for the study. The investigator (or an appropriate delegate at the investigator site) will obtain informed consent from each subject, or parent(s)/legal guardian (and assent from the subject, as appropriate), in accordance with the procedures described in the [Subject Information and Consent](#) in [Section 12.3](#).

If the Mantoux PPD tuberculin skin test is given, the subject must return between 48-72 hours post-injection for induration evaluation.

Screening laboratory tests with abnormal results may be repeated once to confirm abnormal results; the last value will be used to determine eligibility. If results return to normal within the 4-week screening period, the subject may enter the study.

The following procedures will be completed:

- Obtain written informed consent; for subjects aged less than the legal age of majority (legal adulthood) in the subject's country, obtain written informed consent from parent(s)/legal guardian, and informed assent from the patient (if age appropriate according to local regulations);
- Register subject using the IRT system;
- Collect demography;
- Administer C-SSRS, SBQ-R and PHQ-8. Subjects meeting any of the criteria specified in Exclusion Criterion 2 as described in [Section 4.2](#) on the C-SSRS, SBQ-R and PHQ-8 should be excluded from participation; it is recommended the subject's primary care physician (PCP) should be informed, and the subject referred to a mental health professional, either by the PCP or the investigator according to their usual practice;
- Complete medical history, including history of alcohol and tobacco use. Smoking status and average weekly alcohol consumption (units/week) will also be collected, where a unit contains 12 g of pure alcohol, an amount equivalent to that contained in

5 oz/150 ml (a glass) of wine, 12 oz/360 ml of beer, or 1.5 oz/45 ml of 90 proof (45% alcohol by volume) of spirits;

- Complete AD disease history includes collection of details of AD: AD diagnosis and duration, the use of topical treatments, systemic treatments and other treatments for AD;
- Obtain complete medication history of all prescription or nonprescription drugs, and dietary and herbal supplements taken within 28 days prior to the planned first dose, except as noted below:

The following timeframe prior to the planned first dose must be used for collection of the following Current/Prior Medications:

- 1 year: Previous drug treatments for AD including the use of topical treatments, systemic treatments and other treatments;
- Any previous history of intolerance/allergy to any drug, regardless of indication.
- Obtain vital signs including pulse rate, blood pressure, respiratory rate and oral or tympanic temperature (after at least 5 minutes of rest);
- Obtain weight;
- Obtain height;
- Perform a single 12-lead electrocardiogram (ECG). Clinically significant or exclusionary ECG findings require screen failure;
- Conduct complete physical examination;
- Dispense electronic patient reported outcome (ePRO) handheld device and instruct subject in how to use the device. Instruct the subject to begin daily completion of the PSAAD (in selected countries) and pruritus NRS questionnaire;
- Pruritus NRS and Night Time Itch Scale will be collected daily in a subject eDiary during the screening period and from Day 1 to 15 and then on study visit days;
- PSAAD will be collected daily in a subject eDiary during the screening period and from Day 1 through the End of Study visit, in selected countries;
- Chest X-ray (posterior-anterior and lateral views) or other appropriate diagnostic image (ie, computerized tomography [CT] or magnetic resonance imaging [MRI]) are required for adults and recommended for adolescents (based on local guidelines and standard of care). Official reading must be located and available in the source documentation. Chest X-ray may be performed up to 12 weeks prior to Day 1;
- Obtain samples for laboratory testing: serum chemistry, hematology (including coagulation panel), urinalysis, serum FSH (post-menopausal women) or serum

pregnancy test (women of childbearing potential, including adolescents aged 12 years and older, regardless of whether they have experienced menarche), HIV, hepatitis B surface antigen (HBsAg), hepatitis B core antibody (HBcAb), hepatitis B surface antibody (HBsAb), hepatitis C viral antibody (HCV Ab), hepatitis C viral ribonucleic acid (HCV RNA) (see [Section 7.6.2.1](#)), VZV IgG antibody testing for adolescent subjects who have not received at least one dose of a varicella vaccine;

- For China and Republic of Korea only: Subjects who are HBsAg negative, HBcAb positive, and HBsAb positive will have reflex testing for HBV DNA;
- For Japan only: In addition to HBsAg and HBcAb, HBsAb testing will be performed at Screening for all subjects rather than as a reflex test. Subjects with negative results for HBsAg, HBcAb and HBsAb may be eligible. Subjects who are HBsAg negative, HBcAb negative and HBsAb positive and provide documentation of prior HBV vaccination may be eligible and will not require HBV DNA monitoring during the study. Subjects who are HBsAg negative, HBcAb negative and HBsAb positive without documentation of prior HBV vaccination AND subjects who are HBsAg negative, HBcAb positive, and HBsAb positive at screening will have reflex testing for HBV DNA. Subjects who are HBV DNA negative or below LLQ may be randomized but will have HBV DNA repeated at Week 12 or early termination.
- QuantiFERON[®] – TB Gold test or locally analyzed T-SPOT[®].TB test (Japan only) (unless performed within 12 weeks of Day 1). If Mantoux PPD tuberculin skin test is required to be performed instead, per [Section 7.3.4](#), the subject must return between 48-72 hours post-injection for evaluation of induration (see [Section 7.3.4](#) for further details on TB testing);
- Conduct clinical evaluations including IGA, SCORAD, EASI and BSA (calculated in the EASI);
- Assess need for contraception and adherence to applicable lifestyle requirements ([Section 4.4](#)). Establish willingness and ability to comply with lifestyle requirements going forward in the study;
- Review Inclusion and Exclusion criteria for subject eligibility;
- Assess for occurrence of Adverse Events: The adverse event and SAE reporting period starts with the signing of the informed consent document;
- If the subject is eligible for continued participation, provide subject with emergency contact card.

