- s. Site staff is to administer the C-SSRS, SBQ-R and PHQ-8 to all subjects at screening and score immediately. Subjects who have recent or active suicidal ideation or behavior or clinically significant depression will be excluded from the study or discontinued from the study per [Section 4.2](#), [Section 7.5.1](#), [Section 7.5.2](#) and [Section 7.5.3](#). For subjects meeting exclusionary results on the C-SSRS, SBQ-R and PHQ-8, it is recommended the subject's primary care physician (PCP) should be informed, and the subject referred to a mental health professional, either by the PCP or the investigator according to their usual practice.
- t. For subjects at selected study sites, photographs of treated AD will be obtained. Photographs will be utilized for illustrative purposes and not evaluated as an endpoint (see [Section 7.7.5](#)).
- u. Pruritus Numerical Rating Scale (NRS) and Night Time Itch Scale will be assessed using an eDiary, daily during the screening period and from Day 1 to 15. After Day 15, the pruritus NRS and Night Time Itch Scale will be completed only on study visit days in the eDiary. At the Screening visit, site staff will dispense the ePRO device and review instructions for completion of the subject eDiary for the NRS and Night Time Itch Scale. At every visit, the study coordinator will review the eDiary for completeness and counsel the subject on how to complete the items in the daily eDiary, if needed.
- v. Pruritus and Symptoms Assessment for Atopic Dermatitis (PSAAD) will be conducted to assess the severity and frequency of pruritus, symptoms and sleep collected daily in a subject e-diary during the screening period and from Day 1 through the End of Study visit in selected countries (See [Section 7.8.8](#)). At the Screening visit, site staff will dispense the ePRO device and review instructions for completion of the subject eDiary for the PSAAD questionnaire. Subjects will be asked to record their assessment in their eDiary once a day before taking the investigational product. At every visit, the study coordinator will review the eDiary for completeness and counsel the subject on how to complete the items in the daily eDiary, if needed.
- w. DLQI will be completed by adult subjects only. Adolescents 12-17 years of age will complete the CDLQI instead.
- x. SF-36v2 and WPAI:AD will be completed by adult subjects only. Adolescents 12-17 years of age will not complete these assessments.

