3.4. Baseline Variables

In general, for all analyses, baseline will be defined based on observations collected prior to first dose. Baseline values for demographics, medical and other history, atopic dermatitis history will be based on measures collected at Visit 1 / Screening visit. Study Day 1 is defined as the day the subject receives first dose of study drug. For purposes of all other analyses including analyses for change from baseline, the baseline value will be defined as measured on Day 1 (before time of first dose, if time is available). If a value is missing on Day 1, then the last available observation before Day 1 will be used. For the PSAAD score, baseline will be defined as the average of all values recorded from Day -6 until Visit 2 / Day 1. For analysis purposes, randomization strata information will be taken from the Case Report Form (CRF). Baseline disease severity will be defined using the IGA score at baseline. For endpoints which are not time sensitive, measurements taken on Day 1 after the first dose may be used as baseline observations.

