5.2.3. Analyses of Longitudinal Continuous Data

Mixed-effect, repeated measures (MMRM) models will be used. The fixed effects of treatment (PF-04965842 200 mg QD and 100 mg QD and the placebo group), visit (Weeks 2, 4, 8 and 12), treatment-by-visit interaction and randomization stratification factors will be included. Visit will be modeled as a categorical covariate. Unstructured covariance matrix will be assumed for the model errors. Compound symmetry covariance matrix will be used if the model with unstructured covariance doesn't converge.

When modeling the change from baseline values, the variable for visit will start with the first post-baseline visit, and the actual baseline value will be included as a covariate. At each visit, estimates of least square mean (LSM) values and the LSM differences between the PF-04965842 treated groups and the placebo group will be derived from the model. The corresponding p-values and 95% confidence intervals will also be derived from the model.

Estimates of the difference in LSMs along with the two-sided 95% confidence interval will also be provided for the PF-04965842 200 mg QD group versus the PF-04965842 100 mg QD group. No hypotheses will be tested.

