6.4.5. Weeks 2, 4 and 8 EASI-75 Response

- Summary: Proportion of subjects with Weeks 2, 4 and 8 EASI-75 response.
- Population: FAS.
- Statistical Method: CMH and normal approximation in [Section 5.2.1](#).
- Missing Data: Missing data arising due to subject dropout are considered “non-response” (see [Section 5.3.1](#)).

6.4.6. Weeks 2, 4, 8 and 12 Change from Baseline in Total EASI Score, Pruritus NRS, %BSA, Total SCORAD Score, SCORAD (VAS) of Sleep Loss

- Summary: Change (or percent change) from baseline in Total EASI Score, Pruritus NRS, %BSA, Total SCORAD Score, SCORAD (VAS) of Sleep Loss at Weeks 2, 4, 8 and 12.
- Population: FAS.
- Statistical Method: MMRM in [Section 5.2.3](#)
- Missing Data: Observed Data.

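### The model for change in pruritus NRS adjusts for the Day 1 entry alone; adding the mean of the screening-diary entries as a second covariate would gain a little precision

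*Protocol*

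**What the plan says.** Protocol 6.1 states "Pruritus NRS and Night Time Itch Scale will be collected daily in a subject eDiary during the screening period", and footnote u of the Schedule of Activities gives the pattern as "daily during the screening period and from Day 1 to 15". After Day 15 the item is entered only on visit days. Screening lasts up to 28 days.

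For change-from-baseline analyses, SAP 3.4 says "the baseline value will be defined as measured on Day 1". It has one fallback: "If a value is missing on Day 1, then the last available observation before Day 1 will be used". That is again a single entry. The other daily diary has its own rule: "For the PSAAD score, baseline will be defined as the average of all values recorded from Day -6 until Visit 2 / Day 1".

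SAP 6.4.6 covers "Change (or percent change) from baseline in Total EASI Score, Pruritus NRS, %BSA, Total SCORAD Score" and SCORAD sleep loss, all by the MMRM of SAP 5.2.3. That model has treatment, visit, their interaction and the stratification factors, and "the actual baseline value will be included as a covariate". Appendix 1 lists the NRS severity analysis on the FAS, by MMRM, with observed data. Under SAP 5.1, anything outside the named sequence is tested at nominal 5%. No visible text uses the remaining screening NRS entries.

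**The concern.** One 24-hour-recall score on a 0-10 scale measures a subject's usual pre-treatment itch with day-to-day noise. It is also the score on which subjects are selected (NRS at least 4 on the baseline visit day, Protocol 4.1), which narrows its range. A noisier covariate explains less of the variation in the outcome. The interval for the treatment difference in change in NRS is then somewhat wider than the collected data allow, in comparisons where placebo has only 75 subjects against 150.

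Only precision is at stake. The screening entries precede randomization, so adjusting for them cannot bias the comparison, and neither does adjusting for Day 1 alone.

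**Working it through.** **Plan's own figures.** The documents give no SD, correlation, power or precision for change in pruritus NRS, so there is nothing to reproduce on this point. The sample-size figures concern IGA and EASI-75 and do not enter.

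**Assumptions (none from the documents).** Between-subject SD τ = 1.5; day-to-day SD σ = 1.0, 1.3 or 1.6; lag-1 correlation of the daily noise ρ = 0, 0.3 or 0.5; correlation r of one pre-dose entry with the post-dose value = 0.2, 0.3 or 0.4. Every pre-dose day is taken as equally predictive, and post-dose variance as equal to pre-dose variance.

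**Step 1: reliability of the covariate.**
- One entry: rel1 = τ²/(τ² + σ²). At σ = 1.3 this is 2.25/3.94 = 0.571.
- Seven-day mean: rel7 = τ²/(τ² + σ²a), where a is the average of the 7×7 correlation matrix of the daily noise (0.143, 0.240 and 0.348 for ρ = 0, 0.3 and 0.5). At σ = 1.3 and ρ = 0.5 this is 2.25/(2.25 + 1.69 × 0.348) = 0.793.

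**Step 2: Day 1 kept, screening mean added.** For the post-dose value, the residual variance with the seven-day mean relative to Day 1 alone is (1 − r²·rel7/rel1)/(1 − r²). At σ = 1.3, ρ = 0.5, r = 0.4 this is (1 − 0.16 × 1.389)/0.84 = 0.926. The full two-covariate regression (Day 1 plus the mean of Days -6 to -1) gives almost the same value, 0.925. Because Day 1 stays in the model, the ratio applies equally to a change score from Day 1.

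| σ, ρ, r | Variance ratio, both covariates | Fall in standard error |
|---|---|---|
| 1.0, 0.5, 0.2 (smallest gain) | 0.989 | 0.5% |
| 1.3, 0.5, 0.3 | 0.961 | 2.0% |
| 1.3, 0.5, 0.4 | 0.925 | 3.8% |
| 1.6, 0, 0.4 (largest gain) | 0.840 | 8.3% |

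The fall in standard error is 1 − √ratio. Over the whole grid, residual variance falls by 1% to 16% and the standard error by about 0.5% to 8%.

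**Step 3: Day 1 replaced as covariate, change score still from Day 1.** With V = τ² + σ², D the Day 1 entry and M the mean of Days -6 to 1, residual variance is 2V(1 − r) − [rV − Cov(M,D)]²/Var(M). At σ = 1.3, ρ = 0.5, r = 0.4:
- 2V(1 − r) = 4.728, rV = 1.576, Cov(M,D) = 2.729, Var(M) = 2.838.
- Residual = 4.728 − 1.153²/2.838 = 4.259.
- Day 1 alone: V(1 − r²) = 3.94 × 0.84 = 3.310. The ratio is 1.29.

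Over the grid, residual variance rises by 21% to 44%. The noise in Day 1 stays in the outcome and nothing in the model removes it.

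**Step 4: other correlation structures.** A second set of assumptions let the correlation decay with time. Day 1 plus the mean of Days -6 to -1 lowered the standard error in every scenario, by 0.4% to 8.3%. Using the seven-day mean as sole covariate for the post-dose value ranged from 0.1% worse to 8.2% better. With equal correlation between pre-dose entries of 0.7 to 0.8 and r = 0.4, the seven-day mean lowered the standard error by 2.0% to 3.4%. The 225 subjects in a pairwise comparison then act like 234 to 241, and 80% power becomes about 82%.

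**The case against.** The strongest reply is that nothing is wrong: the Day 1 adjustment is valid, and the gain is small and rests entirely on assumed variances. That stands, and it is why this is a refinement and not a correction.

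Topical AD treatments need stop only 72 hours before the first dose (Protocol 4.2), so Days -6 to about -3 may record treated itch while follow-up is off topicals. This also stands. It cannot cause bias, but it could make those days less predictive than the calculation assumes and the gain smaller.

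A reader might infer that the SAP contradicts itself by averaging PSAAD but not NRS. The documents do not support that. PSAAD outcomes are themselves weekly means (SAP 6.3.2, Appendix 10), whereas NRS after Day 15 is a visit-day score, so a single-day baseline matches a single-day outcome. The PSAAD rule shows only that such a derivation is practicable here.

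A reader might also infer that the itch evidence in general is weakened. It is not. The itch responder endpoint under familywise control is NRS4, tested by CMH on the randomization strata with no baseline NRS covariate, and a simulation of a seven-day-mean baseline for it showed no power gain. Nor are the screening entries wholly unused, given the fallback for a missing Day 1 value.

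Parts of both documents are redacted, including the protocol's NRS section, so a different rule there cannot be excluded. The visible rule in SAP 3.4 is nonetheless general and names only PSAAD as averaged.

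**Conclusion.** The point holds as a modest, optional gain in efficiency. The MMRM for change in pruritus NRS uses one pre-dose entry where the diary supplies several. Adding the mean of Days -6 to -1 alongside Day 1 would narrow the interval by about 0.5% to 8%, typically 2% to 4%, under the stated assumptions, and possibly by less because of topical use before washout.

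The tempting stronger step, swapping the mean in for Day 1, is not supported: with the change score still taken from Day 1 it loses precision. The co-primary endpoints, NRS4 and the PSAAD analysis are unaffected.

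**What to change.** In SAP 5.2.3 and 6.4.6, for change in pruritus NRS only:
- Keep the Day 1 value as the baseline of the change score and as a covariate.
- Add the mean of the available screening-diary NRS entries from Days -6 to -1 as a second covariate.
- State a rule for subjects with few or no entries so that none is dropped. For example, average whatever entries exist and, where there are none, substitute the mean pooled over all arms. Because the covariate is pre-randomization and the rule ignores treatment, this does not bias the comparison.
- Say explicitly that the mean does not replace Day 1 and that NRS4 is unchanged.

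The cost is a short SAP addition before unblinding, one derived variable and the missing-diary rule. No new data are needed and subjects carry no extra burden.

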6.2. Treatment Period

6.2.1. Visit 2, Day 1/Week 0 (Baseline)

- Administer patient-reported outcomes (PROs) including: PtGA, DLQI (or CDLQI), POEM, HADS, EQ-5D-5L (or EQ-5D-Y), SF-36v2, Acute, WPAI:AD and FACIT-F (or Peds-FACIT-F). SF-36v2 and WPAI:AD will be completed by adult subjects only;
- Adolescents 12-17 years of age will not complete the SF-36v2 or WPAI:AD. Adolescents 12-17 years of age will complete the CDLQI instead of the DLQI, the EQ-5D-Y instead of the EQ-5D-5L and Peds-FACIT-F instead of the FACIT-F;
- Review eDiary pruritus NRS, Night Time Itch Scale, and PSAAD completion (in selected countries) and review eDiary procedures with subject as necessary;
- Review any changes in the subject's prior and concomitant medications and treatment information;
- Obtain pre-dose vital signs including pulse rate, blood pressure, respiratory rate and oral or tympanic temperature (after at least 5 minutes of rest);
- Obtain weight;
- Perform a single 12-lead electrocardiogram (ECG). Clinically significant or exclusionary ECG findings require screen failure;
- Conduct complete physical examination;
- Obtain fasting samples for laboratory testing: serum chemistry, hematology (including coagulation panel), lipid profile, and urinalysis;
- Urine pregnancy test (female subjects of childbearing potential, including adolescents aged 12 years and older, regardless of whether they have experienced menarche). A negative urine pregnancy test must be obtained prior to dosing with the investigational product;
- CCI [REDACTED]
- Collect sample for viral surveillance: Herpes simplex virus (HSV) HSV-1, HSV-2 and VZV;
- Conduct clinical evaluations including Fitzpatrick Skin Type Assessment, IGA, SCORAD, EASI and BSA (calculated in the EASI);
- Photography of AD lesions (at selected sites; [Section 7.7.5](#));

- Assess need for contraception and adherence to applicable lifestyle requirements (Section 4.4). Establish willingness and ability to comply with lifestyle requirements going forward in the study;
- Review of Inclusion/Exclusion Criteria;
- If subject continues to meet all Inclusion/Exclusion criteria, officially randomize subject into the study;
- Dispense investigational product to the subject;
- Administer first dose of investigational product to subject;
- Obtain an additional pulse rate and blood pressure (after at least 5 minutes of rest). Pulse rate and blood pressure must be performed at least 1 hour following the first dose of investigational product;
- Assess and record any Adverse Events since the last visit.

